12.0 STUDY COMMITTEES AND COMMUNICATIONS

Each of planned study committees will have a charter outlining its activities and responsibilities. In brief, the purpose of each committee is as follows:

- **Independent EAC:** Adjudication of hemostatic efficacy, deaths, TEs, and post-surgical bleeding events for all patients. The EAC will be blinded to all anti-fXa levels.
- **Independent DSMB:** Monitoring of all safety data.

13.0 INVESTIGATOR AND ADMINISTRATIVE REQUIREMENTS

13.1. Institutional Review Board or Independent Ethics Committee

The protocol and ICF for this study must be reviewed and approved by an appropriate IRB or IEC before patients are enrolled in the study. It is the responsibility of the Investigator to assure that the study is conducted in accordance with current country and Local Regulations, ICH, GCP, and the Declaration of Helsinki. A letter, documenting the approval that specifically identifies the protocol by number and title as well as the Investigator, must be received by Portola Pharmaceuticals, Inc. before initiation of the study. Amendments to the protocol will be subject to the same requirements as the original protocol.

After the completion or termination of the study, the Investigator will submit a report to the IRB or IEC, and to Portola Pharmaceuticals, Inc.

13.2. Informed Consent

Each patient must be provided with oral and written information describing the nature and duration of the study, and the patient must sign a written ICF in a language in which he/she is fluent before study-specific procedures are conducted. The signed and dated ICF will be retained with the study records. Each patient will also be given a copy of his/her signed ICF. Due to the critical nature of the illness under study and the possibility that patients will be unable to provide their own consent, proxy consents (defined as consent from a legally authorized representative) and/or emergency consents (defined as consent from a qualified medical professional) are allowed if permissible by local or regional laws and regulations.

13.3. Documentation

The Investigator must provide Portola Pharmaceuticals, Inc. with the following documents (copies of which must be maintained by the Investigator):

1. Curriculum vitae of the Investigator and any sub-investigators listed on the Form FDA 1572.
2. A signed copy of the IRB or IEC approval notice for protocol and informed consent.
3. A copy of the IRB- or IEC-approved ICF.
4. Laboratory certification with a list of normal values for laboratory tests that will be conducted at local laboratories.
5. Completed financial disclosure form for the Investigator and any sub-investigators listed on the Form FDA 1572.

13.4. Data Collection and Management Responsibilities

Data collection is the responsibility of the clinical trial staff at the site under the supervision of the site Investigator. The Investigator is responsible for ensuring the accuracy, completeness, legibility, and timeliness of the data reported.

All source documents should be completed in a neat, legible manner to ensure accurate interpretation of data. Data recorded in the eCRF derived from source documents should be consistent with the data recorded on the source documents.

Clinical data (including AEs, concomitant medications, and expected adverse reactions data) and clinical laboratory data will be entered into a 21 Code of Federal Regulations (CFR) Part 11-compliant EDC system, as appropriate. The data system includes password protection and internal quality checks, such as automatic range checks, to identify data that appear inconsistent, incomplete, or inaccurate. Clinical data will be entered directly from the source documents. Some clinical laboratory data will be collected externally from the EDC systems. Further details for data collection and data handling will be specified in the data management plan, eCRFs, instructions for completing forms, other data handling procedures, and procedures for data monitoring. The MedDRA coding dictionary will be used for coding AEs, medical history conditions, and procedures. The reconciliation of the SAEs between the clinical and safety databases will be conducted as specified in plans determined and approved prior to study start-up. The WHO-DD dictionary will be used to code medications.

13.5. Study Records Retention

Study documents should be retained for a minimum of 2 years after the last approval of a marketing application in an ICH region and until there are no pending or contemplated marketing applications in an ICH region or until at least 2 years have elapsed since the formal discontinuation of clinical development of the study intervention. These documents should be retained for a longer period, however, if required by local regulations. No records will be destroyed without the written consent of the Sponsor, if applicable. It is the responsibility of the Sponsor to inform the Investigator when these documents no longer need to be retained.

13.6. Deviation from the Protocol

The Investigator will not deviate from the protocol. In medical emergencies, the Investigator will use medical judgment and will remove the patient from immediate hazard, and then notify the Portola Pharmaceuticals Medical Monitor and the IRB or IEC immediately regarding the type of emergency and course of action taken. Any action in this regard will be recorded on the appropriate eCRF. Deviations due to non-compliance that render subject non-evaluable for key endpoints will be considered significant deviations. Any other changes in the protocol will be made as an amendment to the protocol and must be approved by Portola Pharmaceuticals, Inc. and the IRB or IEC — before the changes or deviations are implemented.

Portola Pharmaceuticals, Inc. will not assume any responsibility or liability for any deviation or change that is not described as part of an amendment to the protocol.

13.7. Disclosure of Data

Individual patient medical information obtained as a result of this study is considered confidential and disclosure to third parties other than those noted below is prohibited. Patient confidentiality will be further assured by utilizing patient identification code numbers to correspond to treatment data in the computer files. The study personnel, employees of the regulatory agencies, including the US FDA and the study sponsor, Portola Pharmaceuticals, Inc., and its agents will need to review patient medical records in order to accurately record information for this study. If results of this study are reported in medical journals or at meetings, the patient's identity will remain confidential.

13.8. Drug Accountability

The Investigator must maintain accurate records of the amounts and dates andexanet was received from Portola and prepared for the study, including the volume and concentration of stock solution prepared and remaining stock solution volume after dose preparation. All drug supplies must be accounted for at the termination of the study and a written explanation provided for any discrepancies. All partially used or unused drug supplies can be destroyed at the site if available, in accordance with approved written procedures, or returned to Portola Pharmaceuticals, Inc. after written authorization is obtained from Portola Clinical Development. The Investigator will maintain a record of the amount and dates when unused supplies were either destroyed or returned to Portola. All records will be retained as noted in Section 13.5.

13.9. Study Monitoring

The Investigator will allow representatives of Portola Pharmaceuticals, Inc. to periodically review (at mutually convenient times before, during, and after the study has been completed) all eCRFs and relevant portions of office, clinical, and laboratory records for each patient. Appropriate source documents, including documents that support patients' eligibility (e.g., medical history, concomitant medications) should be made available to the study monitor. The monitoring visits provide Portola Pharmaceuticals, Inc. with the opportunity to evaluate the progress of the study; verify the accuracy and completeness of eCRFs; assure that all protocol requirements, applicable regulations, and Investigator's obligations are being fulfilled; and resolve any inconsistencies in the study records.

15.0 LIST OF APPENDICES

Appendix A: Schedule of Activities

Appendix B: Disseminated Intravascular Coagulation (DIC) Scoring Algorithm [8]

Appendix C: Definitions of Cardiogenic Shock, Severe Sepsis and Septic Shock [9]

Appendix D: Definition of Female of Childbearing Potential

Appendix E: Guidance for Submission of Potential Thrombotic Events for Adjudication

Appendix F: American Society of Anesthesiologists Physical Status Classification

Appendix G: Protocol Summary of Changes (Original vs. Amendment 1)

APPENDIX A. SCHEDULE OF ACTIVITIES

STUDY DAY:	Screening & Baseline			Treatment				Follow-Up		
				1				2	3	30 or ET
TIME POINT AND WINDOW:	-2 hours to -45 min	-45 min to -30 min	-30 min to -5 min	End of Bolus +15 min	EoII -15 min	EoS [1] + 15 min [2]	EoS + 12 h ± 1 h	EoS + 24 h ± 1 h	EoS + 72 h ± 1 h	+ 7 days
Obtain Consent	X									
Determine Eligibility	X									
Obtain Medical History	X									
Demographics	X									
Obtain Prior Medications and Time of Last Anticoagulant Dose or Plasma Level	X									
Obtain ASA Class			X							
Vital Signs (BP, HR, RR, temp)	X	X		X	X	X	X	X	X	X
Weight (actual reported/recent)	X									X
Physical Examination	X						X	X	X	X
Central Labs: Anti-fXa and anti-IIa Activity		X (pre-ADX)		X	X	X				
Central Labs: Thrombin Generation		X (pre-ADX)		X	X	X	X	X	X	
Central Labs: Antibodies to andexanet, HCPs, and FX/FXa (modified Bethesda); and nAb (andexanet)	X (pre-ADX)									X
Central Labs: TFPI activity		X (pre-ADX)		X	X	X	X	X	X	
Local Labs: PT-INR	X									

STUDY DAY:	Screening & Baseline			Treatment				Follow-Up		
				1				2	3	30 or ET
TIME POINT AND WINDOW:	-2 hours to -45 min	-45 min to -30 min	-30 min to -5 min	End of Bolus +15 min	EoII -15 min	EoS [1] + 15 min [2]	EoS + 12 h ± 1 h	EoS + 24 h ± 1 h	EoS + 72 h ± 1 h	+ 7 days
Local Labs: Chemistry and Pregnancy Test [3]	X									
Local Labs: CBC		X				X	X			X
Prepare Andexanet	X									
Administer Andexanet Bolus, Immediately Followed by an Infusion			X							
Assess Need for Extended Andexanet Infusion.(if Surgery Ongoing)					X [4]					
Surgical Intervention				SURGERY						
Record Blood Loss Post Surgery						X				
Record Investigator Assessment of Intraoperative Hemostasis						X				
Record Blood Products & Hemostatic Treatments [5]		X								
Record Bleeding-Related Diagnostic & Therapeutic Procedures [6]		X						X	X	
Record Volume of Colloid and Crystalloid [5]		X								
Record Hours in ED, PACU, ICU/Critical Care, General Hospital Floor, and Total as an Inpatient										X

STUDY DAY:	Screening & Baseline			Treatment				Follow-Up		
				1				2	3	30 or ET
TIME POINT AND WINDOW:	-2 hours to -45 min	-45 min to -30 min	-30 min to -5 min	End of Bolus +15 min	EoII -15 min	EoS [1] + 15 min [2]	EoS + 12 h ± 1 h	EoS + 24 h ± 1 h	EoS + 72 h ± 1 h	+ 7 days
Record AEs	X			X				X	X	X
Record Concomitant Medications	X			X				X	X	X
Ascertain Survival Status										X

ADX = andexanet; AE = Adverse event; ASA = American Society of Anesthesiologists; BP = Blood pressure; CBC = Complete blood count; ED = Emergency department; EoII = End of Initial Infusion; EoS = End of Surgery; ET = Early Termination; FX = Factor X; FXa = Activated factor X; h = Hour(s); HCP = Host-cell protein; HR = Heart rate; ICU = Intensive care unit; INR = International normalized ratio; min = Minute(s); nAb = Neutralizing antibody (activity); OR = operating room; PACU = Post-anesthesia care unit; PT = Prothrombin time; RR = Respiratory rate; SoS = Start of Surgery; Temp = Temperature; TFPI = Tissue factor pathway inhibitor

¹ The EoS time point before may occur SoS + 1 hour or SoS + 2 hour; EoS procedures should be carried out when EoS occurs.

² Collect EoS samples within 15 minutes from the end of surgery but before stopping infusion.

³ Pregnancy test in women of childbearing potential; test may be done on urine or serum.

⁴ Approximately 30-45 minutes prior to the end of the andexanet infusion, the investigator should inform the pharmacy whether additional andexanet will be needed, to allow time for preparation.

⁵ Colloid, crystalloid, hemostatic agents, and blood products administered prior to arrival in the ED should also be recorded.

⁶ Record procedures performed to evaluate bleeding source/extent and for treatment of bleeding.

STUDY DAY:	Re-Dose of Andexanet		
	1		
TIME POINT AND WINDOW:	Pre Start of Bolus -15 min	End of Bolus +15 min	Pre End of Infusion -15 min
Initiate Andexanet Low Dose Bolus + Infusion	X		
Central Labs: Anti-fXa and anti-IIa Activity	X (pre-ADX)	X	X

**APPENDIX B. DISSEMINATED INTRAVASCULAR COAGULATION (DIC)
SCORING ALGORITHM [8]**

Note: Algorithm should only be used for patients with an underlying disorder known to be associated with overt DIC. A score of ≥ 5 is compatible with overt DIC.

Laboratory Test	Result	Score
Platelet Count	$\geq 100 \times 10^9 / L$	0
	$< 100 \times 10^9 / L$	1
	$< 50 \times 10^9 / L$	2
D-Dimer, Fibrin Degradation Products	No increase	0
	Moderate increase	2
	Strong increase	3
Prothrombin Time	< 3 seconds	0
	≥ 3 but < 6 seconds	1
	≥ 6 seconds	2
Fibrinogen Level	≥ 1 g/L	0
	< 1 g/L	1

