	
length of the surgery. It is possible that the bolus or continuous infusion may be ongoing at the start of surgery. There are 2 possible dosing regimens as described below:
 

 
Extended Infusion
 
Following the primary andexanet bolus and infusion (~2.5 hours), the andexanet infusion will be continued at the low dose of andexanet (4 mg/min) if the surgery and immediate post-operative period extend longer than the primary bolus and infusion. The extended infusion will continue through the end of the surgery and the immediate post-operative period, not to exceed 6 hours total.
 
Criteria for Re-Dosing with Andexanet
 
Consider re-dosing with andexanet (low-dose bolus + infusion) only if:
 
 a) New, clinically significant, surgery-related post-operative bleeding occurs after initial course of andexanet (primary bolus + infusion and extended dosing, as applicable) is completed, AND b) The treating physician has clinical suspicion that the patient still has levels of FXa inhibition sufficient to contribute to the bleeding, AND c) Re-dosing initiation occurs within 12 hours after the start of the first course of andexanet treatment. 	
lasting at least 120 minutes, irrespective of the length of the surgery. It is possible that the bolus or The continuous infusion may must be ongoing at the start of surgery, and must continue until the end of surgery even if extended treatment is required. There are 2 possible dosing regimens as described below:
 

 
*Extended Infusion (Additional low-dose 4 mg/min infusion up to 4 hours)
 
Following the primary andexanet bolus and 120-minute infusion (~2.5 hours), the andexanet infusion will be continued at the low dose of andexanet (4 mg/min) if the surgery and immediate post-operative period extends longer than the primary bolus and infusion. The extended infusion will (1) must continue at least through the end of the surgery and (2) may additionally continue during the immediate post-operative period, (per investigator discretion), and (3) should not exceed 6 hours.
 
The total duration of dosing including initial bolus, 120-minute infusion, and any extended infusion, should not exceed 6.5 hours. The limit of planned duration of infusion is stipulated to balance declining anti-fXa plasma levels and acceptable exposure to andexanet.
 
Criteria for Re-Dosing with Andexanet
 
Consider re-dosing with andexanet (low-dose bolus + 120 min infusion) only if:
 
 a) New, clinically significant, surgery-related post-operative bleeding occurs after initial course of andexanet (primary bolus + infusion and extended dosing, as applicable) is completed, AND b) The treating physician has clinical 	

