3.4.2 Rationale for the Dose Regimen	
 Low dose: 400 mg IV bolus at a rate of 30 mg/min (duration of approximately 15 minutes) followed by a continuous infusion at a target rate of 4 mg/min for 120 minutes irrespective of the duration of surgery (extended infusion at the discretion of the Investigator). High dose: 800 mg IV bolus at a rate of 30 mg/min (up to 30 minutes) followed by a continuous infusion at a target rate of 8 mg/min for 120 minutes irrespective of the duration of surgery (extended infusion at the discretion of the Investigator). 
Data from the Phase 3 studies with apixaban and rivaroxaban, as well as a recently completed Phase 1 study of Generation 2 andexanet in healthy volunteers (Study 16-512-Direct Inhibitors; Section 1.4.3), confirm the levels of FXa inhibition and recovery of TG observed in the Phase 2 study.
	
 Low dose: 400 mg IV bolus at a rate of 30 mg/min (duration of approximately 15 minutes) followed by a continuous infusion at a target rate of 4 mg/min for 120 minutes irrespective of the duration of surgery (extended infusion at the discretion of the Investigator). High dose: 800 mg IV bolus at a rate of 30 mg/min (up to duration of approximately 30 minutes) followed by a continuous infusion at a target rate of 8 mg/min for 120 minutes irrespective of the duration of surgery (extended infusion at the discretion of the Investigator). 
Extended infusion at the low-dose (4 mg/min) may be administered for up to an additional 4 hours after initial dosing (bolus + infusion) is completed (1) in order to ensure mandatory continuous infusion from start to end of surgery, and (2) may continue into the immediate post-operative coverage per investigator discretion. Total dosing time (initial bolus + 120 minute infusion + any extended infusion) should be less than 6.5 hours.
 
Evidence to support this dosing regimen comes from PK/PD modeling that included results from the ANNEXA-4 study in bleeding patients. Data from the Phase 3 studies with apixaban and rivaroxaban, as well as a recently completed Phase 1 study of Generation 2 andexanet in healthy volunteers (Study 16-512-Direct Inhibitors; Section 1.4.3), confirm the levels of FXa inhibition and recovery of TG observed in the Phase 2
	Included more details about dosing.	NS

		study.		

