	
duration of surgery. The start of the bolus will occur prior to, but not more than 30 minutes before, the start of surgery (i.e., at the first incision). It is possible that the bolus or infusion may be ongoing at the start of surgery. There are 2 possible dosing regimens (Table 2).
 
If the initial andexanet dosing regimen (bolus plus continuous infusion; ~2.5 hours) is completed prior to the end of the procedure, the infusion should continue at a low dose (4 mg/min) through the end of the surgery and the immediate post-operative period. To facilitate the extended infusion, approximately 30 minutes prior to the end of the andexanet infusion, the investigator should inform the pharmacy whether additional andexanet will be needed, to allow time for preparation. The total length of the initial course of andexanet (initial bolus/infusion plus extended infusion) should last no longer than 6 hours.
 
If a post-operative patient meets the applicable criteria for andexanet re-dosing (Table 2), he/she may be re-dosed. All patients that are re-dosed will be administered a low-dose bolus (400 mg) plus continuous infusion (4 mg/min for 120 minutes). If a patient is re-dosed, a baseline anti-fXa activity sample will be drawn beforehand; no post-initiation anti-fXa activity will be obtained.
	
<Figure 3 inserted>
 
Key Dosing Directives:
 
 Initial Bolus (low/high-dose) must be completed prior to start of surgery (initial skin incision) Initial dosing (low/high-dose bolus + 120-min infusion) should be completely administered irrespective of surgery length. Infusion should continue throughout the duration of surgery, defined as skin incision to skin closure. Extended infusion (up to 4 hours at 4 mg/min) (1) may be administered to ensure continuous infusion to match the duration of the surgery, and (2) can additionally proceed into the immediate postoperative period per investigator discretion. 
Initial Dosing (Bolus + 2-hour infusion):
 
The initial andexanet dosing regimen will consist of the following:
 
 1. an IV bolus, (to be completed prior to surgery) 
followed immediately followed by
 
 2. an IV continuous infusion lasting for at least 2 hours, (irrespective of the duration of surgery). 
The start of the bolus will occur prior to, but should be initiated not more than 30 minutes before, and must be completed by, the start of surgery (i.e., at the first incision). The bolus will be followed immediately by a continuous infusion lasting at least 120 minutes, irrespective of the length of the surgery. It is possible that the bolus or infusion may be
	
andexanet dosing rules in relation to surgery timing and procedures.
	

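### Appendix A schedules the extended-infusion assessment at least 15 minutes later than its own footnote wants the pharmacy told; the two times need reconciling.

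*Protocol*

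**What the plan says.** The Amendment 1 schedule in Appendix A has a row headed "Assess Need for Extended Andexanet Infusion.(if Surgery Ongoing". Its only mark is in the fifth time column, which is labelled as 15 minutes before EoII. The abbreviation list gives "EoII = End of Initial Infusion".

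That mark carries footnote 4: "Approximately 30-45 minutes prior to the end of the andexanet infusion, the investigator should inform the pharmacy whether additional andexanet will be needed". The footnote gives the reason as "to allow time for preparation". The change table in Appendix G shows the same lead time as new text for Section 6.2.

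On continuity, the new text listed in Appendix G includes these statements:

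- Synopsis, dosing: the infusion "must continue until the end of surgery even if extended treatment is required".
- Section 3.4.2: extended infusion is allowed "in order to ensure mandatory continuous infusion from start to end of surgery".
- Section 6.2: "Infusion should continue throughout the duration of surgery, defined as skin incision to skin closure", and "Initial dosing (low/high-dose bolus + 120-min infusion) should be completely administered irrespective of surgery length".

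Footnote 2 of the current Appendix A also assumes that the infusion is still running when the end-of-surgery samples are drawn.

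**The concern.** The column and its footnote give two times for one decision. Telling the pharmacy whether more drug is needed presupposes that the need has been judged, yet the schedule puts the judgement after the time for telling. A site cannot keep to both.

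What is at stake is limited but real. If a site works from the column and preparation takes the full lead time, the initial infusion can run out before the extension is ready. In a patient still on the table, that break falls inside the period over which Section 11.5.1 grades hemostasis, which runs from the start of surgery to the end of the procedure. The end-of-surgery anti-fXa sample could then follow an interruption that the regimen did not intend. Longer operations are foreseen: Section 11.9 plans subgroups for surgery of 2 to 4 hours and of more than 4 hours.

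**Working it through.** The plan states no figure to reproduce. The check puts both times on one clock, counted in minutes from the start of the initial infusion.

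**Inputs**

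- Initial infusion: 120 minutes (Section 6.2 new text in Appendix G).
- Pharmacy notice: about 30 to 45 minutes before the end of infusion (Appendix A, footnote 4).
- Assessment: the column 15 minutes before EoII, read either as that time point or as the last 15 minutes of the infusion (Appendix A).
- Bolus: 400 mg or 800 mg at 30 mg/min, started no more than 30 minutes before incision, finished before incision and followed at once by the infusion (Appendix G, dosing text).

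**Do the windows overlap?**

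- Notice: 120 − 45 = 75 to 120 − 30 = 90.
- Assessment: 120 − 15 = 105 to 120.
- Smallest separation: 105 − 90 = 15 minutes. There is no overlap.

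**How long could a break be?** The possible break is the lead time needed minus the time left at assessment. This assumes that notice goes out at assessment and that preparation takes the whole lead time.

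| Lead time needed | Assessed 15 min before the end | Assessed at the end |
|---|---|---|
| 30 min | 30 − 15 = 15 min | 30 − 0 = 30 min |
| 45 min | 45 − 15 = 30 min | 45 − 0 = 45 min |

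At the scheduled time point the result is 15 to 30 minutes. The right-hand column is the extreme, in which nobody assesses until the infusion is ending. If the site follows footnote 4, the break is 0.

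**Which operations are exposed?** At the target rate the bolus takes 400/30 = 13.3 minutes or 800/30 = 26.7 minutes.

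- If the bolus ends at incision, the initial infusion ends 120 minutes after incision.
- If the bolus starts 30 minutes before incision, the initial infusion ends 13.3 + 120 − 30 = 103.3 minutes (low dose) or 26.7 + 120 − 30 = 116.7 minutes (high dose) after incision.

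Any operation lasting more than 2 hours therefore outlasts the initial infusion. The protocol does not say what share of patients that is.

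**The case against.** The best answer is that the operative timing is printed on the same cell. A footnote qualifies the mark it is attached to, so the natural reading is that footnote 4 governs notice and the column is merely the nearest available heading. The logged Section 6.2 text agrees with the footnote. This stands to the extent that a careful site will have no gap. It does not remove the conflict, because following the footnote means assessing before the scheduled column.

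Two further limits also stand. The 30 to 45 minutes is an approximate recommended lead time, not a measured preparation time. The continuity requirement is known mainly through the change table, since the Amendment 1 dosing section is not in the part at hand, and some of that table's wording is softer (the infusion should continue; an extension may be given). Footnote 2 of the current Appendix A is the one current passage that presumes an infusion still running at the end of surgery.

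A reader might infer three stronger things that the documents do not support:

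- **That gaps will occur.** They are possible only at sites that work from the column, and only if the full lead time is needed.
- **That patients in a gap would be without effect, or that the lost effect can be computed from a half-life.** The protocol file gives an effective half-life of 1 to 2 hours (Section 9.2.4.9), one of about 1 hour (Section 7.2.1, September 2019 text) and a terminal half-life of about 8 hours (Section 1.4.4, same text). Nowhere does it say that effect falls in proportion to drug. Section 1.4.5 reports anti-fXa differences from placebo until 2 hours after infusion.
- **That the secondary endpoint is biased.** It is the change to a nadir (Section 11.5.2.2). The samples after the bolus and before EoII precede any such break, and a later, higher value cannot raise a minimum already reached.

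**Conclusion.** The concern holds as an inconsistency within the current schedule. The assessment and the notice that depends on it are at least 15 minutes apart in the wrong order. The consequence is a possible break in infusion during operations that outlast the initial 120 minutes, at sites that act on the column instead of its footnote.

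The 15 to 30 minute figure rests on two assumptions: that notice is given at the scheduled assessment, and that the whole recommended lead time is needed. Any effect on the graded hemostasis or on the end-of-surgery sample is plausible, but its size cannot be established from the protocol. The point is worth correcting because the schedule is what staff work from during surgery and the correction is nearly free.

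**What to change.** Reconcile the Appendix A column, footnote 4 and the Section 6.2 text so that assessment of the need and notice to the pharmacy have one consistent timing, with the assessment no later than the notice that depends on it. Which timing is right is for the sponsor to decide with its sites and pharmacies; this review does not propose one.

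The change is one cell or one footnote, plus a check that Section 6.2 agrees. As a protocol change it needs an amendment under Section 13.6, so it could go in with the next one. Endpoints, sample size and analysis are unaffected.
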